6.2.3 Vital Signs Measurement

Vital signs are to be measured at visits indicated in Appendix A. Refer to the manufacturer's manual for proper operation, calibration, care and handling of the monitor. Select an appropriately sized BP cuff.

For each vital sign measurement, record the patient's position and the arm used for the measurement.

6.2.3.1 Seated Blood Pressure Measurement

Situate the patient in a quiet environment with feet flat on the floor, back against the chair and arm resting on a table or other support so that the midpoint of the cuff is at the level of the heart. The patient must rest for at least 10 minutes in the seated position prior to measuring blood pressure (BP).

6.2.3.2 Standing Blood Pressure Measurement for Orthostatic Assessment

To assess for the presence of orthostatic hypotension, additional BP and pulse rate will be assessed at selected study visits (see Appendix A) or as needed at the discretion of the Investigator. After measurement of seated BP, the patient will change to a standing position. After 2 minutes of standing, BP and pulse rate will be measured three times, with each test separated by at least 1 minute from the prior test. If the diastolic BP readings from the 3 tests are not all within 5 mm Hg, 2 additional standing BP readings must be obtained (total of 5 BP readings), with each test separated by at least 1-minute from the prior test.

6.2.4 Electrocardiogram

A standard 12-lead electrocardiogram (ECG) will be recorded at selected study visits (see Appendix A). Each ECG will be performed in triplicate. A central ECG service will be utilized for reading all ECGs. Refer to the ECG Manual for proper operation, care and handling of the machine.

6.2.5 Physical/Neurological Examination

Neurological examinations include assessment of mental status, level of consciousness, sensory function, motor function, cranial nerve function and reflexes. Neurological examinations will be performed at the times/dates according to the schedule as shown in Appendix A (Schedule of Procedures).

6.2.6 Physical Measurements (Height and Weight)

Height will be measured at Screening in the MAD, Part 1, of the study only. For measurements of body weight, the same weighing scales should be used to weigh a given patient throughout the study. Scales should be calibrated and reliable; scales should be zeroed just prior to each patient's weigh-in session. A patient should void just prior to being weighed. Weight should be recorded before a patient's meal (if applicable) and at approximately the same time of day at each visit. Patients should be minimally clothed (i.e., no shoes or heavy over-garments).

6.2.7 Neuroimaging Assessments

Neuroimaging assessments will be conducted using a 3T MRI scanner or PET scanner.

A 3D T1-weighted structural MR scan will be used to quantitate whole brain, hippocampal, and intraventricular volumes.

MRI safety sequences (T2 FLAIR, GRE T2 star, T2 Fast Spin Echo [FSE]/Turbo Spin Echo [TSE] and DTI) will be performed at Screening and Day 169 in MAD Part 1 and at the Registration Visit (patients who are not seamlessly transitioning to the LTE Part 2 only), Day 252 (or Day 336 if not performed at Day 252) and Day 449 in LTE Part 2, to characterize the patients' pre-treatment and post-treatment state. Safety scans must be reviewed locally by a trained radiologist.

To quantify the CSF volumes of individual patients, an MRI scan of the entire neuroaxis will be obtained at Screening.

Non-ionizing arterial spin labeling (ASL) MRI will be used to quantitate changes in tissue perfusion.

Positron emission tomography (PET) imaging will be used to visualize brain changes; in the MAD, Part 1, of the study PET imaging will only be done in Cohorts C and D, and in LTE, Part 2, of the study PET imaging will be done in all patients. At each PET imaging visit, each patient will undergo PET imaging with only 1 of 2 ligands; either a fluorodeoxyglucose (FDG) tracer will be used to capture the changes of regional metabolism in the brain, or MK6240, a Tau ligand, to capture changes in Tau pathology. For Cohorts C and D, PET imaging will be done 3 times over the course of the study: during the MAD, Part 1 screening window, at the Part 1 Day 169 visit, and at the Part 2 Day 449 visit. For patients from Cohorts A and B returning to participate in Part 2, PET imaging will be at 2 timepoints, during the Part 2 Registration Period and at the Part 2 Day 449 visit. In the event that Tau-PET is either not available at the site or has not yet been approved, then FDG-PET should be performed. As soon as Tau-PET is approved and available at a site, patients should switch to Tau-PET imaging, instead of FDG-PET imaging, for their next scan.

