Appendix A Schedule of Procedures – MAD Part 1, all Cohorts Continued

- 4 APP, PSEN1, PSEN2, APOE, BCHE, IL1RAP and MAPT H1 haplotype (unless tested previously and laboratory report is available for documentation)
- 5 Height measured at Screening only
- Full physical and neurological exam (including fundi) to be given at Screening and abbreviated physical (but full neurological) exam to be given during treatment and follow-up period as indicated to assess changes from Screening. In addition to administration on the visits shown, neurological exam should be conducted if patient experiences an adverse event suggestive of cognitive or motor dysfunction
- 7 Measured in triplicate at the Day 1 visit (pre-dose only)
- 8 Women who are not surgically sterile
- 9 In addition to administration on the visits shown, RBANS and MMSE should be administered if the patient experiences an adverse event suggestive of cognitive or motor dysfunction
- 10 Stored at -80 °C for follow-up exploration of laboratory findings and/or adverse events (e.g., measurement of cytokine and/or chemokine levels, measurement of additional markers of kidney function, measurement of antibodies) in this or subsequent clinical studies of ISIS 814907
- 11 Local laboratory analysis of PT, INR, aPTT, and platelets must be conducted, and results reviewed prior to performing any LP on the next day during the Treatment Evaluation Period or the same day during the Post-Treatment Period. At Screening, analysis of PT, INR, aPTT, and platelets must be conducted and results reviewed within 2 days prior to the Screening LP
- 12 Local analysis of PT, INR, aPTT, and platelets is only conducted at Day 253 (Week 37) in patients who will undergo CSF sampling at this visit if they missed a previous LP during the study
- 13 CSF sampling will be conducted at Day 253 (Week 37) as part of the ET procedures in only those patients who did not complete all previous CSF samplings in the study
- 14 Each patient will undergo PET imaging with either FDG or Tau. FDG-PET will be performed unless Tau-PET is available and has been approved at the site. As soon as Tau-PET is approved and available at a site, patients should switch to Tau-PET imaging, instead of FDG-PET imaging, for their next scan

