- Full physical and neurological exams (including fundi) to be given at Registration and abbreviated physical (but full neurological) exam to be given during treatment and follow-up period as indicated to assess changes from pre-dose exams. In addition to administration on the visits shown, neurological exam should be conducted if patient experiences an adverse event suggestive of cognitive or motor dysfunction
- 7 Measured in triplicate at the Day 1 visit (pre-dose only)
- 8 Each patient will undergo PET imaging with either FDG or Tau. FDG-PET will be performed unless Tau-PET is available and has been approved at the site. As soon as Tau-PET is approved and available at a site, patients should switch to Tau-PET imaging, instead of FDG-PET imaging, for their next scan
- 9 In addition to administration on the visits shown, RBANS and MMSE should be administered if the patient experiences an adverse event suggestive of cognitive or motor dysfunction
- 10 Local laboratory analysis of PT, INR, aPTT, and platelets must be conducted and results reviewed prior to performing any LP on the next day during the Treatment Evaluation Period or the same day during the Post-Treatment Period
- 11 Stored at -80 °C for follow-up exploration of laboratory findings and/or adverse events (e.g., measurement of cytokine and/or chemokine levels, measurement of additional markers of kidney function, measurement of antibodies) in this or subsequent clinical studies of ISIS 814907
- 12 Local analysis of PT, INR, aPTT, and platelets is only conducted at Day 449 (Week 64) in patients who will undergo CSF sampling at this visit if they missed a previous LP during the study
- 13 CSF sampling will be conducted at Day 449 (Week 64) as part of the ET procedures in only those patients who did not complete all previous CSF samplings in the study
- 14 Safety MRI will only be performed at Day 336 if the safety MRI was not performed at Day 252.

Time (in reference to time of ISIS 814907 administration):

- a Pre-dose and 3 hours post IT bolus injection; conduct at 6 hours post IT bolus injection if the patient will be discharged from the clinic on this day (discharge is not permitted on Day 1; discharge is permitted on the other dosing days)
- b 24 hours after prior dose of ISIS 814907
- c Pre-dose, 3 and 6 hours post IT bolus injection
- d Pre-dose
- e Pre-dose, 0.5, 1, 2, 3, 4, 5, 6, 8, and 12 hours post IT bolus injection
- f Pre-dose, 0.5, 1, 2, 3, 4, and 5 hours post IT bolus injection

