3.7.2.3 Positron emission tomography (PET) Analysis

This analysis will be performed on the ITT population for the MAD, LTE, and MAD+LTE Periods.

Patients will undergo FDG-PET or Tau-PET imaging to visualize brain changes. In the MAD Period, PET imaging will only be done in Cohorts C and D, and in the LTE, PET imaging will be done in all patients.

- For Cohorts C and D, PET imaging will be done 3 times over the course of the study: during the MAD screening window, at the MAD Day 169 visit, and at the Day 449 visit in the LTE.
- For patients from Cohorts A and B returning to participate in the LTE, PET imaging will be at 2 time points, during the LTE Registration Period and at the Day 449 visit in the LTE.

If Tau-PET is either not available at the site or has not yet been approved, then FDG-PET should be performed. If Tau-PET becomes available to patients in Cohorts C and D in the MAD, then patients should switch to Tau-PET if there are at least 2 imaging time points remaining to enable longitudinal analyses.

Standard uptake values (SUVs) will be extracted to calculate standard uptake value ratio (SUVR), the ratio of target region SUV to reference region SUVs. SUVR values will be computed for the target ROIs. The SUVR values of ROIs will be used to calculate six composites for FDG- or Tau-PET: frontal, cingulate, medial temporal, temporal, parietal, and occipital. Each composite can be derived by averaging the SUVR values from the individual regions listed in Appendix Table A2 constituting the composite. For Tau-PET, the composites will be obtained using the SUVRs that are calculated using cerebellum ventral as the reference region. For FDG-PET, the composites will be obtained using the SUVRs that are calculated using whole cortex, pons vermis and AD preserved as reference regions, respectively.

In the MAD Period, the actual values of each composite and absolute changes from baseline at Day 169 visit will be summarized using descriptive statistics. The absolute changes from baseline at Day 169 will be compared between each ISIS 814907 treated analysis group and pooled placebo using the using the ANCOVA with baseline value as a covariate or Wilcoxon Rank Sum test, as appropriate. In case of very few evaluable scans, only descriptive summary by visit will be provided and ANCOVA may not be performed.

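### The protocol switches patients to Tau-PET at their next scan and the SAP only when two scans remain; a switch at Day 449 loses the same-tracer change to Day 449, and in Cohorts A and B any same-tracer change

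*Combined protocol and SAP*

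**What the plan says.** Protocol 6.2.7 (Neuroimaging Assessments) allows one tracer per PET visit: "each patient will undergo PET imaging with only 1 of 2 ligands", FDG or the tau ligand. FDG is used where Tau-PET is not yet available or approved. After approval, "patients should switch to Tau-PET imaging, instead of FDG-PET imaging, for their next scan". No minimum number of remaining scans is set.

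Footnote 14 to the Part 1 schedules in Appendix A gives the same instruction: "As soon as Tau-PET is approved and available at a site, patients should switch to Tau-PET imaging". Footnote 8 to schedule A.4, which covers all cohorts in the LTE, repeats it after stating that "FDG-PET will be performed unless Tau-PET is available and has been approved at the site".

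SAP 3.7.2.3 differs. Its rule opens "If Tau-PET becomes available to patients in Cohorts C and D in the MAD" and continues "patients should switch to Tau-PET if there are at least 2 imaging time points remaining to enable longitudinal analyses". It has no switch rule for Cohorts A and B, and none for Tau-PET that first becomes available during the LTE.

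Both documents give the same scan times. Cohorts C and D are scanned at Screening, Part 1 Day 169 and Part 2 Day 449. Cohorts A and B are scanned at LTE Registration and Part 2 Day 449.

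**The concern.** Sites acquire scans under the protocol. The safeguard for longitudinal PET data stands only in the SAP, which does not govern acquisition, and it names only two of the four cohorts.

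FDG measures regional metabolism and the tau ligand measures tau pathology. SAP 3.7.2.3 also uses different reference regions for the two tracers. A difference between an FDG ratio and a tau ratio therefore has no meaning. If the last scan is the first with the new tracer, the missing same-tracer scan cannot be recovered at analysis.

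Change from baseline is the longitudinal PET quantity planned for the LTE and MAD+LTE Periods, and SAP 3.2.1 lists PET among the selected MAD+LTE analyses. The trigger is approval and availability at the site, so any losses would probably group by site and calendar time. That grouping is an inference; the documents do not report it.

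**Working it through.** The plan has no figure to reproduce here. The check lists every tracer sequence that the schedules allow.

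**Inputs**
- Scans per patient, k: 3 in Cohorts C and D, 2 in Cohorts A and B (protocol 6.2.7, SAP 3.7.2.3).
- One tracer per visit, and at most one switch, from FDG to Tau.
- Planned sizes: A 8, B 8, C 12, D 16 (protocol 3.1.1). Cohorts A and B: 8 + 8 = 16. Cohorts C and D: 12 + 16 = 28.
- Baselines: the MAD baseline for the MAD and MAD+LTE Periods (SAP 3.2.3.1). In the LTE Period, the MAD baseline for early starters and the last value before the first LTE dose for late starters (SAP 3.2.3.2).

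**Formulas.** With f FDG scans and t Tau scans, scans remaining at the switch = k − f, and same-tracer pairs = f(f−1)/2 + t(t−1)/2.

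| Cohorts | Sequence | Remaining at switch | SAP condition (k − f ≥ 2) | Same-tracer pairs |
|---|---|---|---|---|
| C, D | FDG-FDG-FDG | no switch | not needed | 3 |
| C, D | Tau-Tau-Tau | no switch | not needed | 3 |
| C, D | FDG-Tau-Tau | 3 − 1 = 2 | met | 0 + 1 = 1 (Tau, Day 169 to Day 449) |
| C, D | FDG-FDG-Tau | 3 − 2 = 1 | not met | 1 + 0 = 1 (FDG, Screening to Day 169) |
| A, B | FDG-FDG | no switch | not needed | 1 |
| A, B | Tau-Tau | no switch | not needed | 1 |
| A, B | FDG-Tau | 2 − 1 = 1 | not met, but the SAP rule does not cover these cohorts | 0 |

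**Effect on the planned outputs**
- FDG-FDG-Tau in Cohorts C and D: the MAD change at Day 169 is kept. The change to Day 449 is lost in the LTE and MAD+LTE summaries, for early and late starters alike, because every earlier scan is FDG.
- FDG-Tau in Cohorts A and B: no change of any kind.
- FDG-Tau-Tau in Cohorts C and D, which both documents direct: no same-tracer change from Screening. The patient drops out of the MAD Day 169 comparison and the MAD+LTE change. Early starters also drop out of the LTE change. Late starters can still use the Day 169 Tau scan as their LTE baseline.
- Cohorts A and B without any switch: they have no Part 1 PET, so the MAD baseline does not exist for this endpoint. As written, PET change is undefined for their early starters in the LTE Period and for all of them in the MAD+LTE Period.

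**Size.** The number of switchers is not given, so the count of affected patients lies anywhere from 0 to 16 in Cohorts A and B and from 0 to 28 in Cohorts C and D, less those who do not enter the LTE. One lost patient is 1/6 = 17% of a full Early Start A or B group (8 × 3/4 = 6 active). The same patient is 1/28 = 3.6% of the pooled 60 mg LTE group (8 + 8 + 12 = 28), which SAP 3.2.2.2 also uses for PET.

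**The case against.** The direct contradiction is narrow. If Tau-PET arrives before the Day 169 scan, two scans remain and the two documents agree. They conflict only for Cohort C and D patients when it arrives after Day 169 and before Part 1 ends. For Cohorts A and B, and for arrival during the LTE, the SAP is silent, which is a gap rather than a conflict. PET is exploratory, one stated aim is to gain experience with such measures, and a late Tau scan serves that aim. The SAP also falls back on description alone when few scans are evaluable. All of this stands, and it limits how much weight the point can bear.

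A reader might infer more than the documents support:
- That a last-scan switcher loses every same-tracer change. This is true only in Cohorts A and B.
- That the placebo comparison is damaged. The only planned PET comparison with pooled placebo is at Day 169, and a Day 449 switch leaves it intact.
- That change from baseline is the only PET output. Actual composite values are summarised too, and the regional ratios are listed.
- That each lost patient costs 17% of the data. That takes the smallest group and ignores the pooled 60 mg group and the option to pool further.
- That the plan means to subtract one tracer from the other. Nothing says so; the SAP simply does not state the rule.

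What remains is that following the protocol defeats the purpose the SAP gives for its own condition.

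**Conclusion.** The point holds as a clarification that should be made, not as a threat to the main conclusions. The protocol and SAP give different switch rules for Cohorts C and D in Part 1, and the SAP has none for Cohorts A and B or for the LTE. A switch at Day 449 costs the change to Day 449 in Cohorts C and D and all same-tracer change in Cohorts A and B. The outputs affected by that switch are exploratory and descriptive, and the total loss cannot be sized from the documents.

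This assumes that sites follow the protocol as written, that at least some sites obtained Tau-PET after a first FDG scan, and that the switch runs only from FDG to Tau. The SAP mentions a UK Amendment 7 that is not among the documents; whether it alters the PET rule cannot be checked.

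**What to change.** **Protocol**, for scans not yet acquired: in 6.2.7, footnote 14 and footnote 8 of A.4, let a patient switch to Tau-PET only if at least two scheduled PET scans remain, and otherwise keep the earlier tracer. This removes FDG-FDG-Tau in Cohorts C and D and FDG-Tau in Cohorts A and B, so every remaining complete sequence has at least one same-tracer pair.

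**SAP 3.7.2.3**, useful whatever has already been scanned:
- Extend the switch sentence to Cohorts A and B and to the LTE.
- State that PET change is computed only between scans with the same tracer.
- Name the Registration scan as the PET reference for Cohorts A and B, who have no Part 1 PET.
- State that FDG-Tau-Tau patients in Cohorts C and D are excluded from change from the Screening baseline, and report their Day 169 to Day 449 Tau change separately. For early starters, label it a post-treatment interval change, not a change from baseline.

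A general rule that the first Tau scan becomes a new baseline would not do. A last-scan switcher has no later scan, and for early starters it would conflict with the MAD baseline in SAP 3.2.3.2.

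The cost is a short protocol clarification, a few SAP sentences and fewer single-time-point Tau scans. The SAP describes Part 1 dosing in the past tense, so the protocol wording may come too late for some scans.

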6.2.8 Collection of CSF

Throughout the study, CSF will be collected at Screening, pre-dose on all Study Drug dosing days in Parts 1 and pre-dose on all ISIS 814907 dosing days in Part 2, and during the Post-Treatment Periods of Part 1 and 2 as described in Appendix A. At Screening, 12 mL of CSF fluid will be collected using the provided LP collection kit. This sample will be utilized for screening tests (A β 42, total tau, and p-tau) and for biomarker testing as outlined in Appendix B.

At CSF collections in subsequent visits, 20 mL of CSF fluid will be collected using the provided LP collection kit to allow for biomarker, safety, and PK testing. Depending on institutional guidelines, local anesthesia may be used for the procedure. Sedation may not be used. Spinal ultrasound may be used for the LP procedure, if deemed necessary, but is not required. Fluoroscopy guidance may be used if attempts at LP without imaging are unsuccessful.

6.2.9 Laboratory Assessments

Laboratory analyte samples will be collected throughout the study. A list of these analytes is contained in Appendix B.

6.2.9.1 Plasma, Serum and Urinalysis Laboratory Assessments

Routine chemistry, hematology and urinalysis panels will be conducted as indicated in the Schedule of Assessments (Appendix A). PK analysis of ISIS 814907 in plasma will be conducted using samples collected as described in Appendices A and C. FSH will be measured at Screening in females who are not documented as surgically sterile.

In addition, assessments of exploratory biomarkers will include neurofilament light chain (NfL), tau, interleukin-6 (IL-6), TNF α and 24S-hydroxycholesterol.

A thyroid panel and levels of uric acid, folate, B12, and homocysteine will be measured at the Screening visit only. Other screening tests include hepatitis, HIV and drug/alcohol tests as shown in Appendix B.

Coagulation tests (prothrombin time [PT], INR and activated partial thromboplastin time [aPTT]) and platelets will be analyzed at the central laboratory, as shown in Appendix A. In addition, for each scheduled LP, local laboratory analysis of PT, INR, aPTT, and platelets must be conducted, and results reviewed prior to performing the LP.

- For dosing visits, collection for local labs may occur on the day prior to dosing at the same time that samples are collected for analysis at the central laboratory
- At Screening, analysis of PT, INR, aPTT, and platelets must be conducted, and results reviewed within 2 days prior to the Screening LP
- For other visits requiring LP (Part 1, Days 113, and 141 for Cohorts A and B, and Days 141 and 197 for Cohorts C and D; Part 2, Day 421), collection for local labs may occur on the day of the LP provided results can be obtained and reviewed prior to performing the LP

Extra serum will be stored at -80 °C for follow-up exploration of laboratory findings and/or adverse events as noted in Appendix A.

6.2.9.2 CSF Laboratory Assessments

CSF will be used for standard laboratory measurement of cells, glucose, protein, albumin and ISIS 814907 concentration analyses. CSF will also be used for determining patient eligibility for the study.

Total tau in CSF is the key exploratory endpoint for the study. Other exploratory CSF biomarkers will be examined. Potential biomarkers include, but are not limited to NfL (a neuronal injury marker); p-tau (a target engagement marker); VILIP1 (a neuronal injury marker); chromogranin B, neurogranin and SNAP25 (synaptic markers); IL-6, TNF α , IL-1 β , MCP-1, S100 calcium binding protein B (S100B) and YKL-40 (innate immune activation markers); C3 and FH (complement); apolipoprotein E and clusterin.

Levels of homocysteine, B12, and folate will be measured at the Screening and Part 1, Day 1 visits only.

Extra CSF will be stored for investigation of possible biomarkers of tauopathy, the PD effects of ISIS 814907, or for profiling of drug binding proteins, bioanalytical method validation purposes, stability assessments, metabolite assessments, immunogenicity assessments (including assay development and validation purposes), or to assess other actions of ISIS 814907 with CSF constituents.

